#### **Secondary objective**

- To find the association of Lewis antigen and ABO blood group phenotypes with smoking, alcohol use, diabetes, hypertension and dyslipidemia.

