## **Sampling:**

- Sample size**

Based on the proportion of Le(a-b-) observed in an earlier publication with 95% confidence level and 90% power, minimum sample size comes to 70 in cases and 140 in control group

$$n = \frac{[Z_{1-\alpha/2} \sqrt{2p(1-p)} + Z_{1-\beta} \sqrt{p_1(1-p_1) + p_2(1-p_2)}]^2}{(p_1 - p_2)^2}$$

- Inclusion criteria:**

- Patients in the age group of 30-55 years at the time of data collection
- Diagnosed with coronary artery disease on the basis of positive changes in coronary angiogram (More than 70% coronary stenosis)

- Exclusion Criteria:**

- Patients with other systemic illnesses like malignancy, autoimmune diseases.
- Patients who are not willing to participate in the study.

- Sampling procedure:**

First 70 cases attending the Cardiology department which satisfy the inclusion and exclusion criteria will be included in the study.

- Method of data collection**

70 cases attending the Cardiology department which satisfy the inclusion and exclusion criteria will be taken as cases. 140 age and gender matched healthy blood donors who are eligible to donate blood as per the inclusion and exclusion criteria of Drugs and Cosmetics Rules, 1945 are taken as controls.

After taking written, informed consent from the patients and blood donors satisfying the inclusion criteria, 3 mL blood is collected from cubital vein in Ethylene Diamine Tetra Acetic acid (EDTA) tubes under aseptic precautions. Samples are collected separately from each CAD patient as well as from blood donors.

Collection of blood samples repeatedly from the same subjects are avoided by personally verifying the subject's demographic profile such as full name, age, address, including hospital registration number and by collecting the blood sample in the required quantity.

Lipid profile values, fasting and post prandial blood sugar values will be collected from the laboratory information system. Blood pressure values will be obtained from the medical record and donor forms.

Diabetes mellitus is defined as fasting serum glucose  $>126$  mg/dL and or the reported use of diabetic medications. Hypertension is defined as systolic blood pressure (BP)  $>140$  or diastolic BP  $>90$  mmHg, or reported use of antihypertensive medications.

Alcohol use pattern is categorised as none, low/moderate use (1–14 drinks/week), and heavy use ( $>14$  drinks/week).

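### Counting any reported antihypertensive use as hypertension can label normotensive cases as hypertensive and bias the secondary phenotype–hypertension association, in a direction that depends on who is analysed

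*Combined protocol and SAP*

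**What the plan says.** The secondary objective is to find the "association of Lewis antigen and ABO blood group phenotypes with smoking, alcohol use, diabetes, hypertension and dyslipidemia". Hypertension is therefore one of five risk factors to be set against phenotype.

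The definition is under Sampling, Method of data collection. It has a blood-pressure limb (systolic above 140 or diastolic above 90 mmHg) and a medication limb, and it ends: "diastolic BP $>90$ mmHg, or reported use of antihypertensive medications". Either limb is sufficient, and neither indication nor start date is mentioned. On the source of the readings the protocol says: "Blood pressure values will be obtained from the medical record and donor forms".

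The two groups differ by design. Cases are enrolled on "positive changes in coronary angiogram (More than 70% coronary stenosis") and attend Cardiology. Controls are "140 age and gender matched healthy blood donors who are eligible to donate blood".

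The proforma serves both groups. Its Investigations page has a yes/no box for hypertension with a yes/no medication box beside it, and no field for drug, indication or start date. An earlier page has a free field for past history.

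The Statistical analysis section plans a chi-square test. Its wording refers to CAD patients, but it does not say whether the risk-factor associations are tested in cases, in donors or in both together. It mentions no stratification by case status.

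**The concern.** A definition that accepts any antihypertensive use works when hypertension is the only likely reason for the drug. Here one group is selected for a disease that may itself be a reason. A normotensive case taking such a drug for CAD meets the definition as written. A control described as healthy has no diagnosed CAD to treat, so the same words can measure different things in the two groups.

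At stake is the phenotype–hypertension result. The error could hide a real association among cases. If the groups are pooled, it could produce one that does not exist.

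**Working it through.** **The plan's own figure.** The only calculated figure is 70 cases and 140 controls at 90% power. It concerns the Le(a-b-) proportion and does not use the hypertension definition. The two proportions behind it are not printed, so it cannot be reproduced; nothing below depends on it except the group sizes.

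**Inputs.** From the documents: 70 cases, 140 controls, and the either-limb definition. Assumed: phenotype shares, true hypertension prevalence, and q, the share of truly normotensive cases recorded as hypertensive through a drug taken for CAD. I take q from 0 to 0.8 for cases and zero for donors.

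**Cases only, prescribing unrelated to phenotype.** With true prevalence p, recorded prevalence is p + (1−p)q. The recorded risk difference is therefore (1−q)(p1−p0). With true odds O1 and O0, the recorded odds ratio is (O1+q)/(O0+q).

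Take p1 = 50% in Le(a-b-) and p0 = 33.3% in other cases, so O1 = 1, O0 = 0.5 and the true OR is 2.0. With 30% of cases Le(a-b-), true overall prevalence is 0.3×0.50 + 0.7×0.333 = 38.3%.

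| q | Le(a-b-) | Other cases | Risk difference | OR | Overall recorded |
|---|---|---|---|---|---|
| 0 | 50.0% | 33.3% | 16.7 points | 2.00 | 38.3% |
| 0.1 | 55.0% | 40.0% | 15.0 | 1.1/0.6 = 1.83 | 44.5% |
| 0.3 | 65.0% | 53.3% | 11.7 | 1.3/0.8 = 1.62 | 56.8% |
| 0.5 | 75.0% | 66.7% | 8.3 | 1.5/1.0 = 1.50 | 69.2% |
| 0.8 | 90.0% | 86.7% | 3.3 | 1.8/1.3 = 1.38 | 87.7% |

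If O1 = O0, the recorded OR is exactly 1 for any q. Within cases, then, this error weakens an association but does not invent one.

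Power, in a second assumed example (50% against 30%, 21 against 49 cases): 36% at q=0, 23% at 0.2, 15% at 0.4, 6% at 0.8. It is low before any misclassification.

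**Cases and donors pooled, no true association.** Let Le(a-b-) be 30% of cases (21 of 70) and 15% of donors (21 of 140), with 30% true hypertension everywhere. The Le(a-b-) subjects are then 21 cases and 21 donors; the others are 49 cases and 119 donors.

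- q=0.4: recorded in cases 0.30 + 0.70×0.4 = 0.58. Le(a-b-): (21×0.58 + 21×0.30)/42 = 0.440. Others: (49×0.58 + 119×0.30)/168 = 0.382. OR = 1.27.
- q=0.8: recorded in cases 0.86. Le(a-b-): 0.580. Others: (49×0.86 + 119×0.30)/168 = 0.463. OR = 1.60.

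**Pooled, true OR 2.0, 30% hypertension in those not Le(a-b-).** With the same phenotype split, the OR rises from 2.00 to 2.43 at q=0.8. If Le(a-b-) is 30% in both groups, it falls from 2.00 to 1.62.

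**Pooled, donors also less hypertensive.** With the 30%/15% split, true OR 2.0 within each group, and hypertension in those not Le(a-b-) of 30% in cases and 5% in donors, the pooled OR is already 2.75 at q=0 and is 2.43 at q=0.8. Pooling without stratification is thus a fault of its own, and the direction in which the drug rule moves the result is not fixed.

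**The case against.** The best case for the plan has four parts.

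*The form may already handle it.* The medication box sits beside the hypertension box, and the diabetes item has the same layout, so staff may read it as medication for hypertension. Past history, hospital number and the medical record are also available. This stands in part. A reader might infer that the error could never be corrected, and the documents do not support that. But nothing says the hypertension box means a prior diagnosis, and the written definition overrides it by making medication use sufficient.

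*The drugs that cases take are not stated.* True, and neither is the time to which reported use refers. The size of the effect is therefore assumed. The gap in the definition is not.

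*Donors face the same definition.* They do, on the same proforma. A reader might infer that no donor could be counted through medication. The donor rules are cited but not reproduced, so that goes too far. What can be said is that healthy donors are unlikely to be treated for CAD.

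*Only a secondary result is touched.* Correct. No adjusted analysis is planned, so harm through hypertension as an adjustment variable would be hypothetical.

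**Conclusion.** The definition as written can record normotensive cases as hypertensive and makes hypertension status non-comparable between cases and donors. The consequence is confined to the phenotype–hypertension part of the secondary objective. The primary phenotype–CAD comparison and the 70/140 sample size do not use this variable.

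Two stronger readings should be resisted. The first is that the association is necessarily diluted. That is certain only among cases with prescribing unrelated to phenotype; pooling can create or inflate an association when Le(a-b-) is commoner in cases, which is the study's own hypothesis. The second is that recorded hypertension in cases would mostly reflect CAD treatment. In the first example, true hypertensives make up 38.3/56.8 = 67% of recorded cases at q=0.3 and 38.3/69.2 = 55% at q=0.5. They fall below half only near the top of the range (38.3/87.7 = 44% at q=0.8).

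All these sizes rest on assumed prevalences, phenotype shares and q. The change is worth making before data collection because it is cheap and the indication may be harder to recover afterwards.

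**What to change.** 1. In the definition under Method of data collection, count medication in both groups only when it is taken for diagnosed hypertension.
2. On the Investigations page of the proforma, reword the box to *On medication for hypertension: yes/no*. State that the diagnosis is established from the hypertension box, past history and medical record.
3. In Statistical analysis, state the population for the secondary objective. Test the phenotype–hypertension association within cases and donors separately, or stratified by case status.
4. Add a sensitivity analysis that does not count medication use alone.

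Items 1 and 2 address the dilution within cases; item 3 addresses the spurious association from pooling. Neither replaces the other. I would not require the hypertension diagnosis to precede the CAD diagnosis, since that would miss hypertension first found at the CAD presentation. Nor would I add an *unknown* class that arises only in cases, which would bring in a new asymmetry.

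Cost: one reworded sentence, one reworded box and a few lines of analysis text. The downside is some reliance on recall or records for the indication. The sensitivity analysis will also miss some people whose treated hypertension is controlled, so it should be read beside the main result and not in place of it.

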Smoking pattern is categorised as Smoker (An adult who has smoked at least 100 cigarettes in his or her lifetime, and who now smokes every day), Ex smoker (An adult who has smoked at least 100 cigarettes in his or her lifetime but who had quit smoking), Never smoker: An adult who has never smoked, or who has smoked less than 100 cigarettes in his or her lifetime.

ABO blood grouping is performed according to department's Standard Operational Procedures (SOP). Commercially available monoclonal blood group antisera are used for forward grouping; for reverse grouping 5% pooled suspension of A, B and O cells are used which are prepared according to SOP.

Lewis antigen typing is done by using monoclonal antisera as per manufacturer's instructions.

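### Smoking and alcohol in cases are classified after CAD diagnosis with no reference date, which weakens the phenotype associations in the secondary objective

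*Combined protocol and SAP*

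**What the plan says.** The secondary objective relates Lewis and ABO phenotypes to smoking, alcohol use, diabetes, hypertension and dyslipidemia. It gives no time to which those factors refer.

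- **Entry of cases** (Sampling, Inclusion criteria): angiographic stenosis above 70% is required, so every interview answer from a case follows the diagnosis. The criteria give a time only for age: "Patients in the age group of 30-55 years at the time of data collection". That sets eligibility and does not date the exposures.
- **Smoking** (Method of data collection): a smoker has reached the lifetime threshold of 100 cigarettes "and who now smokes every day". An ex-smoker is "An adult who has smoked at least 100 cigarettes in his or her lifetime but who had quit smoking". A never smoker is defined by lifetime consumption.
- **Alcohol** (same section): "Alcohol use pattern is categorised as none, low/moderate use" (1 to 14 drinks a week) and heavy use (over 14). There is no period of recall and no class for former drinkers.
- **Glucose and blood pressure**: taken from the laboratory system, and from the medical record or donor form. The plan does not say which reading or date applies. Reported medication also assigns diabetes or hypertension.
- **Proforma**: blanks for tobacco, alcohol and past history, one blank each for BP, FBS and PPBS, and yes/no boxes for medication. It has no field for date of CAD diagnosis, quit date, drinking before diagnosis, or start of medication.
- **Statistical analysis**: chi-square tests. The section does not say whether the secondary objective is analysed in cases, in donors, or in both pooled.

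**The concern.** A coronary diagnosis is a common reason to stop smoking or cut down drinking. When status is recorded after the diagnosis and without a reference date, the classes in cases mix earlier habit with response to the disease. Donors' answers are not disturbed in this way, so the same category means different things in the two groups.

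These variables are the outcomes of the secondary objective, and misclassifying them acts directly on its result. Within cases, if stopping is unrelated to phenotype, the contrast shrinks and the chi-square test loses power. If cases and donors are pooled, the shift occurs in one group only and can produce an association where none exists, provided phenotype frequency also differs between the groups. Unless someone happens to write the dates in free text, the proforma does not allow a later correction.

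**Working it through.** **The plan's own figures.** The plan states no number for the secondary objective. Its sample size ("minimum sample size comes to 70 in cases and 140 in control group") belongs to the Le(a-b-) comparison of cases with controls. It cannot be reproduced because the two proportions are not given, and this point does not change it. All rates below are assumptions chosen to show direction and size.

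**1. Attenuation within cases.** Let p be the proportion smoking daily before diagnosis and q the fraction of case smokers who quit afterwards, the same in each phenotype. The proportion recorded as current smokers is p(1 − q).

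- Reference phenotype: p0 = 0.40, odds 0.40/0.60 = 0.667.
- True OR 2.5: odds 0.667 × 2.5 = 1.667, so p1 = 1.667/2.667 = 0.625.

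| q | recorded p1 | recorded p0 | difference | recorded OR |
|---|---|---|---|---|
| 0 | 0.625 | 0.40 | 0.225 | 2.50 |
| 0.3 | 0.4375 | 0.28 | 0.1575 | 0.7778/0.3889 = 2.00 |
| 0.5 | 0.3125 | 0.20 | 0.1125 | 0.4545/0.25 = 1.82 |

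The ratio of proportions stays at 0.625/0.40 = 1.56. The odds ratio and the difference are what shrink. The same algebra applies to any drinking against none, with q the fraction of drinkers who stopped.

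**2. Loss of power in the 70 cases.** Assume 25% are Le(a-b-) (17.5 against 52.5 people on average), with pre-diagnosis smoking of 60% and 35%; two-sided 0.05.

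| q | OR, current vs not | power |
|---|---|---|
| 0 | 2.79 | 45% |
| 0.2 | 2.37 | 34% |
| 0.4 | 2.12 | 26% |
| 0.6 | 1.94 | 19% |

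An ever/never split does not involve q, because a quitter moves from smoker to ex-smoker and stays an ever smoker. Its odds ratio is the same in every row.

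**3. Spurious association on pooling.** Assume no phenotype-smoking link (45% smoked in every group), and Le(a-b-) in 35% of 70 cases (24.5) and 15% of 140 donors (21). The other phenotypes then number 45.5 and 119. At q = 0.4, recorded smoking in cases is 0.45 × 0.6 = 0.27.

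- Le(a-b-): (24.5 × 0.27 + 21 × 0.45)/45.5 = 0.353.
- Others: (45.5 × 0.27 + 119 × 0.45)/164.5 = 0.400.
- Pooled OR = (0.353/0.647)/(0.400/0.600) = 0.82.

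At q = 0.2 and 0.6 the pooled OR is 0.91 and 0.73. Within cases (0.27 against 0.27) and within donors (0.45 against 0.45) the OR is 1, so stratifying by case status removes the artefact.

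**The case against.** The strongest reply is that the harm is limited and the plan already has some protection. Smoking has three classes, so a recent quitter does not become a never smoker. Diabetes and hypertension can be assigned from reported medication, and the proforma has a past-history blank. The remaining error is attenuation in a secondary objective, under quit rates the documents do not supply.

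Most of this stands, and it sets the limits of the point. It does not remove it. The plan specifies no ever/never analysis. Alcohol has no class that would recover a former drinker. The medication route counts treatment begun after CAD was diagnosed, because neither start date nor indication is recorded.

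A reader might infer more, and the documents do not support it:

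- **That case glucose and pressure are acute or in-hospital values.** The protocol says only that cases attend Cardiology. It does not say whether they are inpatients or outpatients, newly diagnosed or established, and laboratory values may predate enrolment. What can be shown is an undefined measurement time, so no rate of false-positive diabetes can be attached to it.
- **That habitual smoking status is lost altogether.** Only the current/former distinction is blurred.
- **That the smoking-CAD association is distorted.** Recorded current smoking in cases would be too low, but neither objective estimates that association.
- **That the variables are spoiled as confounders.** No adjusted model is planned.

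**Conclusion.** The point holds for smoking and alcohol: they are classified after diagnosis in cases, without a reference date, and alcohol has no former-drinker class. Under the stated assumptions, a within-case current-smoking OR of 2.5 reads as 2.00 (30% quitting) or 1.82 (50%). This assumes quitting is equally frequent across phenotypes; if it is not, the bias could go either way. A spurious association requires two further conditions: unstratified pooling, and a phenotype frequency that differs between cases and donors.

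For diabetes and hypertension the supported finding is narrower. The reading to be used is undefined, and treatment started after the CAD diagnosis counts. Ever/never smoking and the primary phenotype-CAD comparison are unaffected. The change is worth making because it is cheap and the missing dates are hard to recover later.

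**What to change.** In Method of data collection and on the proforma:

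1. Classify smoking and alcohol in cases as of just before the first CAD symptom or diagnosis, and in donors as of the donation date.
2. Add fields for date of CAD diagnosis, quit date and drinking before diagnosis.
3. For diabetes and hypertension, record whether the diagnosis or medication preceded CAD. State one rule for which glucose and blood pressure reading is used, applied alike to cases and donors. A rule for cases alone would create a new asymmetry.

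In Statistical analysis:

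4. Report ever/never smoking beside the three classes.
5. Analyse the secondary objective stratified by case/control status.

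The cost is a few proforma fields and reworded questions, with no new test, visit or change in sample size. The downside is some recall error about habits before diagnosis.

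### The smoking classes count only cigarettes, so a person who smokes only other products is coded a never smoker; current non-daily smokers and drinkers averaging under one drink a week fit no class

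*Combined protocol and SAP*

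**What the plan says.** The definitions stand under Sampling, in the text on method of data collection. There are three smoking classes:

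- The class for current smokers requires two things, a lifetime count and a present habit: "An adult who has smoked at least 100 cigarettes in his or her lifetime, and who now smokes every day".
- The class for former smokers applies the same cigarette threshold to people who have since stopped.
- The unexposed class has two limbs joined by *or*, and it reads as follows: "Never smoker: An adult who has never smoked, or who has smoked less than 100 cigarettes in his or her lifetime".

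No equivalence is given for any other smoked product.

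For alcohol, "Alcohol use pattern is categorised as none, low/moderate use (1–14 drinks/week), and heavy use" is completed by a heavy class above 14 drinks a week. No averaging period is stated.

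Both variables are named in the secondary objective: "To find the association of Lewis antigen and ABO blood group phenotypes with smoking, alcohol use, diabetes, hypertension and dyslipidemia". The Statistical analysis section plans frequencies and percentages per category and a chi-square test. The proforma has a tobacco field and an alcohol field under personal history.

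**The concern.** A chi-square table needs classes that cover everyone and that put exposed people on the exposed side. The smoking rule falls short on both counts. Its second never-smoker limb moves a daily smoker of, say, bidis, cigars or a pipe into the unexposed class, and it leaves the current non-daily smoker without a class. The alcohol rule falls short on coverage alone, because nothing lies between none and 1 drink a week.

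Two of the five variables in the secondary objective are therefore at stake. Misclassified smokers dilute the comparison of smoking between phenotypes. For people with no class, the plan does not say whether they are to be left out or placed by judgement.

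**Working it through.** **No stated figure depends on these classes.** The one design figure, "with 95% confidence level and 90% power, minimum sample size comes to 70 in cases and 140 in control group", is based on the Le(a-b-) proportion. The two proportions are not printed, so it cannot be re-derived, and nothing below needs it.

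**Step 1: apply the smoking rule literally.**

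| Person | Class under the rule |
|---|---|
| Smokes bidis daily, 0 lifetime cigarettes | Never smoker |
| Former bidi smoker, 0 lifetime cigarettes | Never smoker |
| Smokes bidis daily, 100 or more lifetime cigarettes | Smoker |
| Current non-daily smoker, 100 or more lifetime cigarettes | None |

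The third row is a Smoker because the daily-smoking condition is not limited to cigarettes. The fourth row fails Smoker (not daily), Ex smoker (has not quit) and Never smoker (too many cigarettes).

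**Step 2: apply the alcohol rule literally** (drinks divided by weeks, with 4.345 weeks to a month).

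| Pattern | Drinks per week | Class |
|---|---|---|
| 1 a month | 1 / 4.345 = 0.23 | None of the three |
| 2 a month | 2 / 4.345 = 0.46 | None of the three |
| 1 every two weeks | 1 / 2 = 0.5 | None of the three |
| 6 a month | 6 / 4.345 = 1.38 | Low/moderate |
| 4 every two weeks | 4 / 2 = 2.0 | Low/moderate |

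The gap is an average above 0 and below 1 drink a week.

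**Step 3: size for smoking, on assumed inputs.** Let p0 be true ever-smoking in the reference phenotype and p1 in the other, with a true odds ratio of 2.0. A share f of ever-smokers is coded never smoker, equally in both phenotypes. Observed prevalence is p × (1 − f), and the odds ratio is recomputed from it.

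With p0 = 0.30, the odds are 0.30 / 0.70 = 0.4286. Doubled they are 0.8571, so p1 = 0.8571 / 1.8571 = 0.4615.

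| f | Observed p0 | Observed p1 | Odds ratio | Prevalence ratio |
|---|---|---|---|---|
| 0 | 0.300 | 0.4615 | 2.00 | 1.538 |
| 10% | 0.270 | 0.4154 | 1.92 | 1.538 |
| 20% | 0.240 | 0.3692 | 1.85 | 1.538 |
| 40% | 0.180 | 0.2769 | 1.75 | 1.538 |

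For p0 = 0.20 the odds ratios at 10%, 20% and 40% are 1.95, 1.91 and 1.83. For p0 = 0.40 they are 1.88, 1.79 and 1.65. The full range is 1.65 to 1.95. The prevalence ratio stays fixed because (1 − f) cancels.

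**Step 4: the equal-share assumption.** Keep p0 = 0.30. If 40% are missed in the reference phenotype and 10% in the other, the odds ratio is (0.4154 / 0.5846) / (0.18 / 0.82) = 0.7105 / 0.2195 = 3.24. With the shares swapped it is (0.2769 / 0.7231) / (0.27 / 0.73) = 0.3830 / 0.3699 = 1.04. The direction of bias therefore depends on the shares being similar.

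**Step 5: power, on separate assumed inputs.** Take 70 + 140 = 210 subjects, 20% of them Le(a-b-) (42 against 168), true smoking 45% against 30%, and two-sided alpha 0.05.

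| f | Odds ratio | Power |
|---|---|---|
| 0 | 1.91 | 0.46 |
| 10% | 1.84 | 0.41 |
| 30% | 1.73 | 0.32 |
| 50% | 1.65 | 0.24 |

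**The case against.** The strongest reply is that the consequence is small and its size rests on nothing in the documents. No section mentions bidis, cigars, pipes or a product mix. The variables serve only the secondary objective, and no adjustment of the primary analysis uses them. Even with 40% missed, the base case moves an odds ratio of 2.0 only to 1.75. All of this stands and sets the weight of the point. It does not remove the misclassification, which follows from the rule as written.

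Several stronger readings are tempting, and the documents do not support them:

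- *Every daily bidi smoker is coded a never smoker.* Only those with under 100 lifetime cigarettes are.
- *Anyone drinking less often than once a week is left out.* The classes count drinks, not occasions, so four drinks every two weeks is low/moderate use.
- *Every association of phenotype with smoking is pulled toward no effect.* With equal missed shares the odds ratio shrinks but the prevalence ratio does not. If the missed share is also equal in current and former smokers, the contrast between those two classes is unbiased. With unequal shares across phenotypes the bias can go either way.
- *The proforma cannot support the classes.* Its tobacco field appears to be open, so product and amount may be written there, and layout may have been lost in conversion from PDF. All that can be said is that the text shows no dedicated item for them.
- *Definitions cited from a cohort of HIV-infected and uninfected men are unsuitable here.* Borrowing categories from another cohort is ordinary practice, and the citation alone shows no fault.

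**Conclusion.** The point holds on the literal definitions. People who smoke or smoked only non-cigarette products are coded never smokers, current non-daily smokers with 100 or more cigarettes have no class, and neither do people averaging above 0 but below 1 drink a week. The smoking part carries the weight, because there a stated rule puts exposed people in the unexposed class. The alcohol gap alone would be close to a missing detail.

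The likely effect is a modestly reduced smoking odds ratio and some loss of power. On the assumptions in the working, an odds ratio of 2.0 appears as 1.92 to 1.75 when 10% to 40% of ever-smokers are missed. That rests on an assumed smoking prevalence, an assumed product mix and an equal missed share across phenotypes, none of which the documents supply. The primary objective and the stated sample size are untouched. This is a cheap improvement, not a threat to the study's main result.

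**What to change.** 1. In all three smoking classes, replace *100 cigarettes* with *100 cigarettes, bidis or other smoked tobacco products*. State how cigars and pipes are counted.
2. Define Smoker as now smoking every day or on some days, or add a separate class for current non-daily smokers.
3. On the proforma, record the product smoked and whether 100 lifetime cigarettes were reached, with smokeless tobacco as a separate item.
4. Define low/moderate alcohol use as *more than 0 and up to 14 drinks/week*, averaged over a stated period.

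The cost is the wording of two definitions and about one line on the form, best done before data collection because product and amount may not be recoverable later. The classes become slightly less comparable with the cited definitions. The plan's own smoking classes can still be derived if the cigarette history and the daily or non-daily pattern are recorded.
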